7 PHARMACOVIGILANCE

7.1 Adverse Event (AE)

An AE is any untoward medical occurrence in a patient or clinical trial subject administered a medicinal product and which does not necessarily have a causal relationship with this treatment. An AE can therefore be any unfavourable and unintended sign (including an abnormal laboratory finding), symptom, or disease temporally associated with the use of the trial medication, whether or not considered related to the IMP.

7.2 Adverse Event recording

For the purposes of the study, AEs will be followed up according to local practice until the event has stabilised or resolved, or the Follow-up Visit, whichever is the sooner. SAEs will be recorded throughout the study.

Non serious AR/AEs

All such toxicities, whether expected or not, should be recorded in the adverse event section of the relevant case record form within one month of the form being due.

(i) Severity of Adverse Events

Definitions for assessment of severity:

Mild:Awareness of event but easily toleratedModerate:Discomfort enough to cause some interference with usual activitySevere:Inability to carry out usual activity

(ii) Causality of Adverse Events

The assignment of the causality should be made by the investigator responsible for the care of the participant using the definitions listed below. If any doubt about the causality exists the local investigator should inform the study coordination centre who will notify the Chief Investigator. The pharmaceutical companies and/or other clinicians may be asked to advise in some cases.

In the case of discrepant views on causality between the investigator and others, all parties will discuss the case. In the event that no agreement is made, the MHRA will be informed of both points of view.

Definitions for assessment of causality:

- Unrelated: No evidence of any causal relationship Unlikely: There is little evidence to suggest there is a causal relationship (e.g. the event did not occur within a reasonable time after administration of the trial medication). There is another reasonable explanation for the event (e.g. the patient's clinical condition, other concomitant treatment).
- Possible: There is some evidence to suggest a causal relationship (e.g. because the event occurs within a reasonable time after administration of the trial medication). However, the influence of other factors may have contributed to the event (e.g. the patient's clinical condition, other concomitant treatments).
- Probable: There is evidence to suggest a causal relationship and the influence of other factors is unlikely.
- Definite: There is clear evidence to suggest a causal relationship and other possible contributing factors can be ruled out.

7.3 Abnormal Laboratory Test Results

Abnormalities in liver function tests and HBV DNA will not be recorded as adverse events. All other clinically important abnormal laboratory test results occurring during the study will be recorded as adverse events. The clinically important abnormal laboratory tests will be repeated at appropriate intervals until they return either to baseline or to a level deemed acceptable by the investigator or until a diagnosis that explains them is made.

7.4 Serious Adverse Events (SAE)

i) Definition of SAE

An SAE is defined as any event that

- Results in death;
- Is life-threatening*;
- Requires hospitalisation or prolongation of existing inpatient's hospitalisation**;
- Results in persistent or significant disability or incapacity;
- Is a congenital abnormality or birth defect;

* "Life-threatening" in the definition of "serious" refers to an event in which the subject was at risk of death at the time of the event; it does not refer to an event which hypothetically might have caused death if it were more severe.

** "Hospitalisation" means any unexpected admission to a hospital department. It does not usually apply to scheduled admissions that were planned before study inclusion or visits to casualty (without admission).

Medical judgement should be exercised in deciding whether an adverse event/reaction is serious in other situations. Important adverse events/reactions that are not immediately life-threatening, or do not result in death or hospitalisation but may jeopardise a subject, or may require intervention to prevent one of the other outcomes listed in the definition above should also be considered serious.

(ii) Reporting of SAEs

Rapid reporting of all SAEs i.e. within 24 hours, occurring during the study must be performed as detailed in the study specific SAE reporting instructions. An overview of the Safety Reporting Process is detailed in the diagram below. If the investigator becomes aware of safety information that appears to be drug related, involving a subject who participated in the study, even after an individual subject has completed the study, this should be reported to the Sponsor.

[figure not shown]
All SAEs will be reviewed by the Chief Investigator or a designated medically qualified representative to confirm expectedness and causality.

Reporting of SAEs and review by the CI will be via the trial data collection system (InForm eCRF).

Fatal or life threatening SAEs should be reported on the day that the local site is aware of the event. The SAE form asks for nature of event, date of onset, severity, corrective therapies given, outcome and causality (i.e. unrelated, unlikely, possible, probably, definitely). The responsible investigator should assign the causality of the event. Additional information should be sent within 5 days if the reaction has not resolved at the time of reporting.

An SAE form should be completed and entered into the eCRF for all SAEs within 24 hours. This will automatically send alert emails to the Chief Investigator, the Project Manager and the Sponsor.

Safety Reporting Overview

* Unless identified in the protocol as not requiring immediate reporting

Contact details for reporting SAEs and SUSARs

Follow the study specific procedure for reporting SAEs and SUSARs and complete an SAE form & submit to the Study Coordination Centre as soon as possible (within 24 hrs). SAE forms are available on the InForm eCRF system.

E-mail: [contact]

(iii) Definition of an Adverse Reaction (AR)

All untoward and unintended responses to an IMP related to any dose administered or relating to the withdrawal of the patient from nucleos(t)ides. All AEs judged by either the reporting investigator or the sponsor as having reasonable causal relationship to a medicinal product qualify as adverse reactions. The expression reasonable causal relationship means to convey in general that there is evidence or argument to suggest a causal relationship.

Exaggerated hepatitis flares are defined according to the following criteria:

- 1. Disturbance of liver synthetic function
 - a. Bilirubin > 35 uMol/l
 - b. INR > 1.3
- 2. ALT > 20 x upper limit of normal

- 3. If HBV DNA and/or ALT remain persistently elevated for more than 6 months
- 4. If, in the opinion of investigator or patient there is a risk to health

These are an expected reaction to nucleos(t)ide withdrawal and will not be recorded or reported as an AR/AE. Exaggerated flares will be recorded in the Case Report Form to monitor patient safety throughout the trial as described elsewhere in the protocol.

Expected non-serious side effects of interferon (as documented in the SMPC) will not be recorded as adverse reactions.

(iv) Definition of a Serious Adverse Reaction (SAR)

A SAR is defined as a SAE that is judged to be related to any dose of study drug administered to the subject or withdrawn from the subject.

(v) Definition of Suspected Unexpected Serious Adverse Reaction (SUSAR)

Any SAR that is NOT consistent with the applicable product information as set out in the Investigator Brochure (IB) or Summary of Product Characteristics (SPC) ie is unexpected.

An unexpected reaction to nucleos(t)ide withdrawal is defined as one which has temporal or biological relationship to the intervention but does not include a hepatitis flare.

(vi) Reporting of SUSARs

In the case of suspected unexpected serious adverse reactions, the staff at the site should:

Complete the SAE eCRF (within 24 hours). The study coordination centre will be notified by email and may contact the local site for further information and may require anonymised copies of all relevant investigations and documents.

Or

Contact the study coordination centre by phone and complete the SAE form within the following 24 hours as above.

The study coordination centre will notify the MHRA, REC and the Sponsor of all SUSARs occurring during the study according to the following timelines; fatal and life-threatening within 7 days of notification and non-life threatening within 15 days. All investigators will be informed of all SUSARs occurring throughout the study.

Local investigators should report any SUSARs and / or SAEs as required by the protocol and study specific SOPs. Follow up of patients who have experienced a SUSAR should continue until recovery is complete or the condition has stabilised.

(vii) Annual reporting of Serious Adverse Events

Annual Safety reports will be submitted to the Sponsor, the Ethics Committee and Regulatory Authority in accordance with regulatory requirements.

(viii) Pregnancy

If a patient becomes pregnant during the study then they will be withdrawn from interferon treatment and encouraged to resume nucleos(t)ide analogues. The outcome of the pregnancy will be reported.

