2.4 Secondary Endpoints

Efficacy endpoints

- The proportion of patients who achieve HBsAg loss who also have undetectable HBV DNA
- The proportion of patients in each group who become inactive HBV carriers; ie achieve a sustained virological response (HBV DNA < 2000 IU/mI & normal ALT values) at 3 years after randomisation
- Magnitude of reduction in quantitative HBsAg levels at 1, 6, 12, 24 & 36 months after randomisation
- Magnitude of changes in antiviral T cells response at 1, 5, 6, 12, 24 & 36 months after randomisation
- Magnitude of changes in NK cells response at 1, 5, 6, 12, 24 & 36 months after randomisation

Safety endpoints

• Proportion of patients in each group with exaggerated hepatitis flares

- Proportion of patients resuming nucleos(t)ide analogue therapy
- Adherence to pegylated interferon therapy

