3 STUDY DESIGN

3.1 Pilot Phase

A pilot phase will be conducted at the beginning of the trial. This will consist of 50 patients recruited across 4 sites. Milestones within the pilot are based on numbers of patients recruited as well as safety aspects/numbers of exaggerated flares as shown in the flow diagram below. The pilot phase will be conducted according to the same protocol as the main trial and the pilot phase patients will count towards the overall trial sample size. Exaggerated flares are defined in Section 6.4 (i).

The milestones for the pilot phase are as follows:

- If the pilot phase fails to recruit 40 patients in 4 months then NIHR-EME will discontinue the study.
- If more than 40% of patients in either arm of the trial experience exaggerated flares by the end of the pilot phase then that arm will be discontinued. If this occurs in the interferon arm then the interferon arm will be modified to a control and combined interferon treatment protocol in which pegylated interferon is added to the nucleos(t)ide analogue for 16 weeks prior to cessation of therapy rather than leaving a gap between nucleos(t)ide analogues withdrawal and pegylated interferon treatment (and compared to the control arm still) see Figure 2. If this occurs in the control arm then the control arm will be switched to the interferon and combined interferon treatment protocol (and compared against the standard interferon arm) see Figure 3.
- If more than 60% of patients in the pilot experience exaggerated flares the trial will be discontinued.
- If more than 40% of patients in both arms experience exaggerated flare by the end of the pilot phase then the trial will be terminated if the DMEC and TSC recommend so.

A safety assessment will be made by the TSC and DMEC when all pilot patients will have completed initial screening, therapy gap and two months of interferon therapy. The trial will be assessed against the above milestones and a decision on the continuation of the trial made.

NUC-B	PROTOCOL Version 2.0 12 th Aug 2016	Sponsor Imperial College	
		impenal College	

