4 PARTICIPANT ENTRY

4.1 Study population

Subjects for the trial will be recruited from hepatology or hepatitis specialist clinics where appropriate patients are already being monitored on treatment with nucleos(t)ide analogues. By definition these patients are strongly adherent with clinic appointments and antiviral drugs. Patients will be given a patient information sheet and invited to an appointment at least one week later.

The trial will be open to patients with HBeAg negative chronic HBV infection who have been treated with nucleos(t)ide analogues for a minimum of three years with HBV DNA < 400 IU/ml for a minimum of two years. After screening all patients will be monitored for 4 - 12 weeks to confirm they continue to meet the inclusion criteria as listed below.

(i) Inclusion criteria

- Age ≥ 18
- Chronic HBV infection
- HBeAg negative
- Nucleos(t)ide analogues treatment for ≥3 years
- HBV DNA < 400 IU/mI ≥2 years
- Informed consent

(ii) Exclusion criteria

- Cirrhosis at any time
- HBeAg to anti-HBe seroconversion within the last 3 years
- Interferon use in the last 3 years
- Contraindications to interferon use
- Participation in HBV-specific therapeutic vaccine studies within 12 months
- HCV, HDV or HIV co-infection
- Immunosuppressant use
- Contraindications to interferon use including:

- The presence of, or history of severe psychiatric condition, particularly severe depression, suicidal ideation or suicidal attempt
- Presence of or history of psoriasis
- Platelet count < 90000/mm³
- Absolute Neutrophil count < 1500/mm³
- Uncontrolled thyroid function
- Pregnancy or breastfeeding
- Women of child-bearing potential not using an effective method of contraception
- Men not using an effective method of contraception
- Clinically significant comorbidities that, in the opinion of the investigator, render the patient unsuitable.

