6.5 Discontinuation of Study Treatment and Withdrawal from Study

(i) Recommencement of nucleos(t)ide analogues

Retreatment with nucleos(t)ide analogue therapy will be recommenced according to the following criteria for exaggerated flares:

- 1. Disturbance of liver synthetic function
 - a. Bilirubin > 35 uMol/l
 - b. INR > 1.3
- 2. ALT > 20 x upper limit of normal
- 3. If HBV DNA and/or ALT remain persistently elevated for more than 6 months
- 4. If, in the opinion of investigator or patient there is a risk to health

It is possible that there may be variation in the criteria used to determine whether a patient with hepatitis flare post cessation would need to be restarted on treatment according to criteria number 4. Data will be collected on patients considered for retreatment to determine whether any systematic differences appear between the two groups.

Recommencement will not be considered as a withdrawal from the study. A form will be completed in the eCRF to document the date and reason for recommencement. Patients who resume nucleos(t)ide analogue therapy will be monitored at intervals at unscheduled visits until ALT, Bilirubin and INR test results begin to normalise and once they have returned to normal then the patients will return to the study visit schedule until the end of the study.

(ii) Permanent discontinuation of study treatment

Subjects may discontinue study medication for the following reasons:

- At the request of the subject.
- Adverse event/ Serious Adverse Event
- Allergic reaction to IMP
- In the event of pregnancy
- If the investigator considers that a subject's health will be compromised due to adverse events or concomitant illness that develops after entering the study.

(iii) Withdrawal from Study

Withdrawal from the study refers to discontinuation of study treatment and study procedures and can occur for the following reasons:

- Subject decision
- Loss to follow-up

In this situation the patient will be encouraged, where possible, to resume the nucleos(t)ide analogue treatment which they were taking before enrolling in the study.

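### Exaggerated-flare limits for bilirubin and INR ignore baseline, eligibility does not cap either, and Section 6.4 conflicts with 6.5(i) and 7.4(iii) on what the pilot's 40% rule counts

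*Protocol*

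**What the plan says.** Protocol Section 7.4(iii) introduces its list with "Exaggerated hepatitis flares are defined according to the following criteria". The items are:

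- disturbed liver synthetic function, given as "Bilirubin > 35 uMol/l" and an INR above 1.3;
- "ALT > 20 x upper limit of normal";
- "If HBV DNA and/or ALT remain persistently elevated for more than 6 months";
- the opinion of the investigator or the patient that health is at risk.

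The same section treats these events as an expected reaction to withdrawal and keeps them out of adverse event recording. Section 6.5(i) repeats the list as the retreatment rule: "Retreatment with nucleos(t)ide analogue therapy will be recommenced according to the following criteria for exaggerated flares". No item in either place refers to a baseline value or to a change.

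Section 4.1 sets limits for HBV DNA, platelets and neutrophils and excludes cirrhosis. It sets none for bilirubin, INR or ALT. The nearest item is discretionary: "Clinically significant comorbidities that, in the opinion of the investigator, render the patient unsuitable".

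The count is used in two main places. Section 2.4 has the safety endpoint "Proportion of patients in each group with exaggerated hepatitis flares". Section 3.1 has the pilot rule, which replaces an arm: "If more than 40% of patients in either arm of the trial experience exaggerated flares by the end of the pilot phase". The pilot has 50 patients, and Table 1 puts 25 in each arm.

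Section 6.4 defines a hepatitis flare as ALT above twice the upper limit of normal. It reaches an exaggerated flare only when such a flare gets worse and meets the definition. Section 3.1 cites a Section 6.4(i) for that definition and Section 8.2(iv) cites Section 6.4. There is no 6.4(i), and 6.4 holds no list.

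**The concern.** A patient may enter with a long-standing raised bilirubin, or with an INR raised for a reason unrelated to hepatitis B. Read on their own, 6.5(i) and 7.4(iii) class that patient as having an exaggerated flare although nothing changed after withdrawal. The event is then attributed to withdrawal, enters the safety endpoint and the DMEC reports, and uses up part of the 40% allowance in an arm of 25.

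The protocol appears to assume normal starting values without securing them. Section 6.5(i) returns retreated patients to the visit schedule once ALT, bilirubin and INR are normal again, which a patient abnormal from the start might never achieve. Section 7.3, for other laboratory tests, does accept a return to baseline.

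The data needed to tell old from new are already collected: the visit tables in Section 5.3 mark liver function tests and prothrombin time at both screening and baseline. What is at stake is the reading of a safety endpoint and a rule that can change a treatment arm during the trial.

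**Working it through.** **Stated figures.** The protocol gives no calculation behind the 40% limit. Its one computed figure, 109 per arm for 40% against 20% at 90% power and two-sided 5%, reproduces exactly without continuity correction. This point does not depend on it.

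**Trigger.** More than 40% of 25 means more than 10 patients, so at least 11 (11/25 = 44%). One patient is 1/25 = 4 percentage points.

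**Method.** Let p be the true rate of new exaggerated flares by the pilot review. Let k be the number in an arm already beyond a bilirubin or INR limit before withdrawal and counted because of it. The arm triggers if at least 11 − k of the other 25 − k have a new flare:

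P(trigger) = P(X ≥ 11 − k), X ~ Binomial(25 − k, p).

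For example, at p = 0.30, k = 0 gives P(X ≥ 11 | 25) = 0.098 and k = 1 gives P(X ≥ 10 | 24) = 0.153.

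The documents give neither p nor k. Both are assumptions, shown over a range:

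| True rate p | k = 0 | k = 1 | k = 2 | k = 3 |
|---|---|---|---|---|
| 20% | 0.6% | 1.3% | 2.7% | 5.6% |
| 25% | 3.0% | 5.5% | 9.6% | 16.2% |
| 30% | 9.8% | 15.3% | 22.9% | 32.9% |
| 35% | 22.9% | 31.3% | 41.4% | 52.6% |
| 40% | 41.4% | 51.1% | 61.2% | 71.0% |

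**As a share rather than a count.** If a share q of patients is beyond a limit at entry, the observed rate is 1 − (1 − q)(1 − p). At p = 30%, the chance per arm goes from 9.8% to 12.8% (q = 2%), 18.3% (q = 5%) or 29.8% (q = 10%). At p = 20% it goes from 0.6% to 1.0%, 2.2% or 6.4%.

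**Can baseline cases trigger the rule alone?** With q = 8%, the expected number is 0.08 × 25 = 2. The chance of 11 or more from these cases only, P(X ≥ 11 | 25, 0.08), is about 1 in a million. They cannot in practice.

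**Which reading governs.**

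| Section | What it implies |
|---|---|
| 6.5(i), 7.4(iii) | Meeting a listed item is enough; no ALT flare is required first |
| 6.4 | An exaggerated flare is an ALT flare that has worsened |
| 3.1, 8.2(iv) | Point to 6.4 for the definition, but the list is not there |

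On the first reading, a stable raised bilirubin or INR with normal ALT counts. On the second it does not. The list does not fit the second reading neatly either, since HBV DNA alone can meet its third item and opinion alone its fourth.

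**The case against.** The best counter-argument is Section 6.4. If an exaggerated flare must be a worsened ALT flare, an isolated old abnormality of bilirubin or INR is never counted. That is a fair reading, and it rules out saying flatly that such patients are counted. It does not settle the matter: the two sections that hold the list state no ALT condition, and the references to 6.4 lead to no list. The ALT threshold in 6.4 also has no baseline clause, although the need for worsening narrows what could be counted under it.

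The number affected may also be small. Cirrhosis is excluded, virus must have been suppressed for at least two years, and the investigator may exclude significant comorbidity. This stands, and it is why the size is given only as a range.

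Counting every patient who crosses a fixed limit can be defended as a cautious safety rule, and the DMEC could look up entry values. But the protocol does not present the rule that way, and it attributes these events to withdrawal. Tabulating abnormal entry values is ordinary SAP content. The counting rule itself is in the protocol and acts during the pilot, so a later SAP cannot be relied on to correct it.

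Three stronger inferences are not supported:

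- A reader might infer that entry abnormalities could by themselves replace an arm. The calculation shows otherwise.
- A reader might put the persistent-elevation item in the same class. It has no numeric limit and needs more than 6 months. The pilot review falls about 12 weeks after baseline for the last patient (a 4-week gap plus two months of interferon), so only early recruits could meet it by then.
- A reader might infer that the comparison between arms is seriously diluted. Under the share model a difference shrinks by the factor 1 − q: at q = 5%, 10 points become 10 × 0.95 = 9.5.

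**Conclusion.** The point holds for bilirubin and INR. As 6.5(i) and 7.4(iii) are written, a patient already beyond either limit before withdrawal counts toward the safety endpoint and the 40% pilot rule, and nothing in 4.1 prevents such a patient from entering. Section 6.4 supports a different count, and the cross-references do not decide between them.

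The effect is modest and depends on how close the true rate is to the limit. One such patient in an arm adds 15.3 − 9.8 = 5.5 percentage points to the chance of triggering at a true rate of 30%, 51.1 − 41.4 = 9.7 at 40%, and 1.3 − 0.6 = 0.7 at 20%. This rests on assumed values of the true rate and of the number affected, on independent patients, and on 25 per arm.

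**What to change.** For the endpoint and the pilot count only:

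1. Count a bilirubin or INR criterion when it is new, or has worsened, relative to that patient's screening and baseline values. State in advance how worsening is judged.
2. List patients already beyond either limit at screening or baseline separately, by arm, for the DMEC.
3. Reconcile Sections 3.1, 4.1, 6.4, 6.5(i), 7.4(iii) and 8.2(iv) on whether an ALT flare must come first, and correct the references to 6.4 and 6.4(i).

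No threshold, eligibility limit or retreatment rule is proposed here; those are for the sponsor to settle.

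The cost is a wording change, with no new data collection. The downside is that the count becomes slightly less conservative, and it can differ from the number of patients retreated under the same list. Reporting both numbers side by side would make that difference visible.

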2.2 Secondary Objectives

- 1. To explore the safety of nucleoside withdrawal
- 2. To explore whether using interferon therapy in conjunction with treatment cessation is safe
- 3. To compare the number of patients in each treatment arm who become inactive HBV carriers.
- 4. Identification of virological and immunological biomarkers which predict a group of patients in which the loss of HBsAg is feasible
- 5. Correlate changes in HBsAg quantification and/or HBsAg status with innate and adaptive immune responses to HBV
- 6. To identify changes in immunological responses to HBV which occur after treatment withdrawal and after sequential NUC/IFN treatment

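### Protocol Sections 7.2 and 7.4(iii) conflict on recording expected non-serious interferon effects, and the flare exemption in 7.4(iii) has no seriousness limit to square it with 24-hour SAE reporting

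*Protocol*

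**What the plan says.** **Interferon effects.** Under its sub-heading for non-serious reactions and events, Protocol Section 7.2 states: "All such toxicities, whether expected or not, should be recorded in the adverse event section of the relevant case record form". Section 7.3 leaves abnormal liver function tests and HBV DNA out of adverse event recording, then adds: "All other clinically important abnormal laboratory test results occurring during the study will be recorded as adverse events". Section 7.4(iii) states: "Expected non-serious side effects of interferon (as documented in the SMPC) will not be recorded as adverse reactions". Section 2.2 lists as its second secondary objective: "To explore whether using interferon therapy in conjunction with treatment cessation is safe".

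**Exaggerated flares.** Section 7.4(iii) defines these by raised bilirubin or INR, ALT above 20 times the upper limit, HBV DNA or ALT elevated for more than 6 months, or a perceived risk to health. It then says: "These are an expected reaction to nucleos(t)ide withdrawal and will not be recorded or reported as an AR/AE". The next sentence provides separate capture: "Exaggerated flares will be recorded in the Case Report Form to monitor patient safety throughout the trial as described elsewhere in the protocol".

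**Serious events.** Section 7.4(ii) says: "Rapid reporting of all SAEs i.e. within 24 hours, occurring during the study must be performed". It repeats the duty for the form: "An SAE form should be completed and entered into the eCRF for all SAEs within 24 hours".

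**The concern.** There are two separate faults, both in rules that fix which data exist. An analysis plan cannot recover an event that was never entered.

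The first concerns fairness between the arms. The trial is open label, the investigator assigns causality (Section 7.2(ii)), and only one arm receives interferon. An exemption for expected interferon effects can therefore remove events from that arm only. The named safety endpoints in Section 2.4 are flares, resumption of nucleos(t)ide analogues and adherence. None of them measures non-serious interferon toxicity, so the adverse event record is its main source. Tolerability matters here: Section 8.1 justifies the assumed benefit partly by reference to interferon's side effects.

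The second concerns prompt reporting. An exaggerated flare can also be a serious event. If a site relies on the flare exemption and files no SAE form, the automatic alert to the Chief Investigator, Project Manager and Sponsor is not triggered.

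**Working it through.** No sample size, power or event figure is involved, so the check sets the rules side by side.

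**1. An expected, non-serious symptom in each arm**

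| Patient | Section 7.2 | Section 7.4(iii) |
|---|---|---|
| Interferon arm, attributed to interferon | Record | Do not record as an adverse reaction |
| Control arm, no interferon given | Record | Exemption does not apply, so record |

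The rules agree for the control patient and disagree for the interferon patient. If all sites follow 7.2, there is no imbalance. If all follow 7.4(iii), events are removed from the interferon arm alone. If sites differ, completeness varies by site.

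**2. Can the two rules be read together?** One could record the complaint as an adverse event but not label it a reaction. The text does not clearly allow this. The sub-heading in 7.2 covers reactions and events together, and 7.4(iii) defines a reaction as an adverse event judged to have a reasonable causal relationship to the product. The exempted item is thus a subset of what 7.2 says to enter.

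**3. Laboratory effects.** Section 6.3, on toxicity, anticipates falls in neutrophils and platelets during interferon. Under 7.3, a clinically important fall is an adverse event, with no exception for expected interferon effects. Under 7.4(iii), an expected and non-serious one is not recorded as a reaction. The same uncertainty arises.

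**4. Exaggerated flares against the SAE rule**

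- The interferon exemption is limited to non-serious effects. The flare exemption, in the same subsection, has no such limit.
- Section 7.4(i) treats an event as serious if it is fatal, life-threatening or requires admission. It also asks that an event which may jeopardise the subject, or need intervention to prevent such an outcome, be considered serious. The fourth flare criterion, a risk to health, can overlap with that.
- Section 7.4(ii) allows no exception in its text. A footnote to the safety reporting overview excepts events that the protocol identifies as not needing immediate reporting.
- Section 7.4(v) leaves hepatitis flare out of the unexpected reactions to withdrawal, so the SUSAR route does not catch a serious flare.

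A site with a serious flare therefore finds one rule telling it to report within 24 hours and another telling it not to record or report the event as an adverse event. Nothing ranks them.

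**5. Scale.** Section 5 expects up to 45% of patients to be retreated: 0.45 × 240 = 108 patients, or 0.45 × 120 = 54 per arm if the rates are equal. The retreatment criteria in Section 6.5(i) are the exaggerated-flare criteria, so the exempt category may be large. The documents do not give the share that would be serious.

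**The case against.** **The safety objective is largely served by other data.** This stands. Exaggerated flares go in the CRF and to the Data Monitoring Committee by arm (Section 8.2(iv)). The date and reason for recommencement are collected (6.5(i)), as are adherence and dose reductions (6.1), and SAEs are recorded throughout (7.2). Serious or unexpected interferon effects are not exempt. A reader might infer that secondary objective 2 cannot be answered. The documents do not support that: what is at risk is the completeness and balance of expected non-serious effects.

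**The tilt is not built in.** This also stands. It arises only where sites follow 7.4(iii) over 7.2, and Section 2.4 lists no comparison of adverse event rates as an endpoint.

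**There is no waiver for serious flares.** A reader might infer that the protocol excuses them from 24-hour reporting. It does not say so. The SAE duty is stated twice for all SAEs, the exemption names reactions and adverse events but not SAEs, and the definition of a serious adverse reaction in 7.4(iv) includes reactions to withdrawn drug. The diagram carrying the footnote and the study-specific SAE instructions are not available here. What remains is an unresolved conflict, which those instructions might settle but the protocol does not.

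**Serious flares would not be seen only at six-monthly committee meetings.** Correct. Unscheduled visits (6.4, 6.5) and the pilot safety assessment (3.1) are further routes. Neither is a substitute for an SAE report.

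**Collecting less for a licensed product is a legitimate choice.** It can be, if stated consistently. Here it contradicts 7.2, and a rule tied to interferon attribution still filters one arm only.

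**Conclusion.** Both conflicts are in the text and should be corrected. On interferon effects, 7.2 and 7.4(iii) give opposing instructions. Where the second is followed, the non-serious tolerability record is incomplete and favours interferon. On flares, the exemption lacks a seriousness limit and leaves open a reading under which a serious flare gets no SAE report.

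Neither effect can be sized from the documents. The 108 patients are an upper figure for retreatment and do not count serious flares. Likewise, the 120 × 16 = 1,920 planned injections in the interferon arm measure exposure and not lost events. The conclusion assumes that some sites would act on 7.4(iii) as worded and that no other trial instruction overrides it. The safety objective is weakened, not defeated. Correction is still warranted, because it protects patients, keeps the arms comparable and costs little.

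**What to change.** Amend the protocol in two places.

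1. Reconcile Sections 7.2, 7.3 and 7.4(iii) into one recording rule applied identically in both arms. The simplest way is to delete the interferon sentence in 7.4(iii) so that 7.2 governs, keeping the exclusion of liver function tests and HBV DNA in 7.3. If relief is wanted for expected non-serious events, confine it to expedited reporting and leave recording intact.
2. Add to the flare exemption in 7.4(iii) that a flare meeting any criterion in 7.4(i) is recorded and reported as an SAE within 24 hours. Check that the overview footnote and the study-specific SAE instructions agree.

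The cost is a short amendment and more adverse event entry at sites during the 16 weeks of interferon. No dose, retreatment or stopping rule changes.
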